5.0 Study Procedures

Procedure/Activity	Frequency
Survey (patient participants and SPs)	Baseline, 6mo, 9mo, 15mo
A1c test (patient participants)	Baseline, 6mo, 9mo, 12mo, 15mo
Diabetes educational materials (patient participants and SPs)	Baseline and quarterly (4x per year)
FAMS 2.0 mobile phone intervention (patient participants)	Approx. 2 texts per day for 9 months
FAMS 2.0 mobile phone intervention (SPs)	Approx. 4-5 texts per week for 9 months
FAMS 2.0 phone coaching (patient participants)	Approx. 25-30 min. calls once a month for nine months

All data were stored in REDCap. Information collected as part of regular care was collected from patient participants' EMR (e.g., birthdate, gender, A1c test results, height, weight, BMI, medications, co-morbidities, etc.). Surveys were administered to all participants at baseline, 6, 9, and 15 months—online, mailed copy, or by telephone. A1c results were collected from persons with diabetes with each survey as well as at 12 months. Participants received mail-in HbA1c test kits provided by CoreMedica Laboratories. HbA1c values collected as part of clinical care were also extracted from the EMR.

Patient participants assigned to control group:

Text messages - Patient participants received a text message when their A1c result was ready (baseline, 6mo, 9mo, 12mo, 15mo).

Patient/SP dyads assigned to FAMS intervention:

Phone coaching - Patient participants completed a phone coaching session with a trained coach once a month for nine months (10 total sessions; 9 core sessions and a brief 10th wrap-up session). Coaching sessions lasted 25-30 minutes each. Coaching sessions included:

- Setting a behavioral goal that can be completed at least 4 days per week in the categories of dietary behavior, physical activity, or stress management (setting and/or adjusting the goal, check in on goal progress)
- Skill building around family/friend involvement in diabetes management, specific to the goal (discussion of helpful and/or harmful family involvement, coach-selected skill building to align with and address the patient participant's experiences, setting a verbal contract to practice the learnt skill with a specific identified person and – at subsequent sessions – check in on how that went).

FAMS 2.0 (PI: [name])

R01-DK119292

NCT04347291

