7.0 Study Withdrawal/Discontinuation

During the enrollment phase, persons with diabetes who did not return their baseline survey after 5 weeks and were unresponsive to research staff communication were administratively withdrawn. If persons with diabetes were not reached for their condition assignment call within one month, then they and their support person (if applicable) were administratively withdrawn.

If a participant expressed wishes to withdrawal from the study, study staff would contact the participant. Study staff followed a protocol to determine which levels of participation the patient does/does not want:

- (1) limited intervention (e.g., no text messages but willing to complete coaching if so assigned) but will complete study assessments
- (2) no intervention (opt out of all assigned study components) but will complete study assessments
- (3) no surveys but okay with completing A1c kits or vice versa and receiving assigned components
- (4) no surveys nor A1c tests but will allow study staff to review and extract relevant data to the study from their EMR
- (5) no further participation

If a SP expressed that they did not want to participate in the study, study staff followed a protocol to determine what level of participation they do/do not want:

- (1) limited intervention – no text messages but will complete study assessments
- (2) no surveys but okay with receiving text messages
- (3) no further participation

Patients can still engage with all aspects of the study if their SPs withdraws. If the patient withdraws to the level of no further participation, their SP would be administratively withdrawn. If a SP withdraws to the level of no further participation, we would contact their patient partner to let them know their SP has withdrawn completely from the study. If a support person withdraws for any reason, the patient participant could identify another support person to participate in the study with them.

If a participant expressed wishes to withdrawal and could not be reached by study staff to confirm their level of withdrawal, the participant was treated as a full withdrawal with no further participation (option 5 from the list above.)

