**Version date 11/20/2023**

## Statistical Analysis Plan for NCT04347291

Our conceptual framework is shown in **Figure 1**. Outcomes include patient participants' HbA1c (primary), diabetes distress and well-being (secondary). Our intervention targets include three hypothesized mediators for patient participants: improved diabetes self-efficacy, improved diabetes self-care behaviors (i.e., dietary behavior, physical activity, and medication adherence), and improved diabetes-specific involvement from family and friends (i.e., increased helpful involvement and reduced harmful involvement). Potential moderators of patient participants' effects are gender, minority race/ethnicity, socioeconomic disadvantage, and support person cohabitation.

Primary support person outcomes are support burden and diabetes distress. Our intervention targets/hypothesized mediators for support persons are self-report on diabetes-specific support provided to the patient participant (i.e., increased involvement, increased helpful involvement and reduced harmful involvement). Exploratory analyses test if improvements in support person outcomes are mediated by improvements in patient participant outcomes (i.e., HbA1c, diabetes distress, well-being). Support person gender and cohabitation are potential moderators of support person effects.

**Figure 1. Conceptual Framework.** FAMS 2.0, Family/friend Activation to Motivate Self-Care version 2.0 evaluated in this study.

Intention-to-treat principles will be used to analyze all available data with two primary models: repeated measures regression models (generalized estimating equations; GEE) to assess main effects and subgroup effects, and structural equation modeling (SEM) techniques to test mediation. To address missing data, we use multiple imputation via chained equations with a total of M=500 iterations. One imputation model includes baseline, 6- and 9-month data during the intervention and a second imputation model includes baseline and 12- and 15-month data for sustained effects.

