To estimate FAMS' main effects and subgroup effects, we will use generalized estimating equations (GEE) with a working-independence correlation structure and identity link. Models will be adjusted for insulin use at baseline and baseline value of the outcome of interest (via a restricted cubic spline with three knots) for each model. We will allow a two-way interaction between time and condition and a two-way spline interaction between time and baseline value of the outcome. Differences between arms will be tested based on a linear combination of regression coefficients at each time point (based on Wald-based test with one degree of freedom). Point estimates and corresponding 95% confidence intervals will be obtained for each follow-up time point, to graphically display trajectories in adjusted mean outcomes difference over 15 months. We will explore subgroups effects (i.e., divided sample) to determine for whom the intervention was most or least effective using the same models as described above.

For each intervention target (**Figure 1**), we fit models as described above. Continuous measures were analyzed using the GEE model. The summative one-item physical activity measure was ordinal, and therefore analyzed using an ordinal regression model (odds ratios obtained on cumulative logit/proportional odds scale). Each model was run three times, to

estimate during (6-months), post (9-months) and sustained (15-months) intervention effects.

For mediation analyses, we model between-subjects mediation with path analysis with an SEM framework as suggested in **Figure 1**, including multiple mediators. Mediation models include intervention targets at both 6 and 9 months as mediators and a single outcome (i.e., HbA1c, diabetes distress or well-being). We ran this model separately for each outcome at 9, 12 (H1cA1c only) and 15 months. For parsimony, we restricted the number of mediators guided by findings evaluating intervention effects on these mediators, opting for continuous and sensitive mediator measure(s) of self-care behaviors unless both measures were significantly improved by the intervention. We used Amos version 29 regression imputation function to address missing data, running each imputation separately for each model.

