Path coefficients and indirect effects evaluate mediation using 2,000 bootstrap samples for bias-corrected estimates and 95% confidence intervals for effects. Paths from condition to mediators will determine if FAMS 2.0 improved each mediator relative to control, and indirect effects will identify mechanisms by which FAMS 2.0 affected outcomes. In addition to examining mediators of patient participants' outcomes, we examine dyadic mediation by assessing whether support person outcome changes are explained by change in their own involvement and/or by improvements in the patient participants' outcomes (e.g., mediator: change in patient participant HbA1c, outcome: change in support person well-being).

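### The mediation models appear to treat regression-imputed values as observed data, so some path intervals are too narrow, and the SAP does not reconcile this with its M=500 multiple-imputation rule

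*SAP*

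**What the plan says.** The SAP's missing-data paragraph opens with "Intention-to-treat principles will be used to analyze all available data with two primary models" and names these as GEE, for main and subgroup effects, and SEM, for mediation. It then gives one rule: "To address missing data, we use multiple imputation via chained equations with a total of M=500 iterations". Two imputation models follow. One holds baseline, 6- and 9-month data; "a second imputation model includes baseline and 12- and 15-month data for sustained effects".

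The mediation paragraph uses targets at 6 and 9 months as mediators of a single outcome: "We ran this model separately for each outcome at 9, 12 (H1cA1c only) and 15 months". For missing data it says: "We used Amos version 29 regression imputation function to address missing data, running each imputation separately for each model". The next paragraph adds: "Path coefficients and indirect effects evaluate mediation using 2,000 bootstrap samples for bias-corrected estimates and 95% confidence intervals for effects".

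In Protocol 5.0, "A1c results were collected from persons with diabetes with each survey as well as at 12 months", and HbA1c may also come from the medical record. Protocol 7.0 lets a participant choose "no surveys but okay with completing A1c kits or vice versa and receiving assigned components", or drop both surveys and kits while still allowing record extraction.

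**The concern.** Regression imputation, read naturally, replaces a missing value by its prediction. If the completed file is then bootstrapped, every resample treats those predictions as data. The bootstrap sees the full sample size and a residual variance that is too small, so it cannot reflect the uncertainty of the imputation. The SAP describes nothing that would put it back.

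The two missing-data statements also need reconciling. The M=500 rule comes straight after SEM is named, yet the mediation paragraph uses another method without saying that it replaces the rule, or why. Nor could the general rule be applied as it stands: neither imputation model joins the 6- and 9-month mediators to the 12- and 15-month outcomes.

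The SAP uses the paths from condition to judge whether each mediator improved, and the indirect effects to name mechanisms. Intervals that are too narrow overstate the evidence for both.

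**Working it through.** **Inputs.** Protocol 8.0: 334 enrolled, about 15% dropout, effective size 284, difference 0.5, SD 1.5, and 80–90% retention for secondary outcomes and mediators (10–20% missing). Protocol 4.0: 1:1 allocation. The documents give no missingness pattern, path sizes or correlations for the mediation models; those below are assumptions.

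**The plan's own figures.** n per arm = 2 × (1.96 + 0.842)² × 1.5² / 0.5² ≈ 141.3, so 142 per arm and 284 in all. 334 × 0.85 = 283.9. The detectable standardized effect is 2.80 × √(2 / n per arm): 0.343 at 80% retention (133.6 per arm) and 0.323 at 90% (150.3 per arm). These agree with the protocol. The documents state no coverage figure for the mediation intervals.

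**Closed form.** Let a fraction m of a path's dependent variable be filled with fitted values, with the predictors observed or filled alongside it so that the estimate is that of the observed cases.

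- True SE ∝ σ / √(N(1−m)), because only observed cases carry information.
- In the completed file the filled cases have zero residual, so the residual variance is about (1−m)σ² and the sample size is N. The estimated SE ∝ σ√(1−m) / √N.
- Estimated SE / true SE = 1−m, so coverage = 2Φ(1.96(1−m)) − 1.
- m = 10%: 2Φ(1.764) − 1 = 92.2%. m = 15%: 2Φ(1.666) − 1 = 90.4%. m = 20%: 2Φ(1.568) − 1 = 88.3%.

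**One-mediator simulation.** N=334; paths 0.33 (condition to mediator), 0.30 (mediator to outcome) and 0.10 (direct); missing completely at random; predicted values filled in once; 2,000 bias-corrected bootstrap samples; 1,500 trials per cell; Monte Carlo SE about 0.6–0.9 points for the affected paths. Coverage (%) at 10/15/20% missing:

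| Missing | Condition to mediator | Mediator to outcome | Indirect effect |
|---|---|---|---|
| Mediator and outcome together | 91.0/89.2/87.3 | 94.6/95.2/95.0 | 92.1/91.9/90.1 |
| Outcome only | 94.4/93.9/94.7 | 91.0/89.6/87.5 | 92.9/93.7/93.3 |
| Mediator only | 92.0/90.0/89.5 | 88.3/82.4/74.7 | 91.1/89.4/86.9 |

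In the last row the mediator is predicted partly from the outcome, so the mediator-to-outcome path is also biased: mean 0.33/0.35/0.37 against a true 0.30.

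**Two-mediator simulation, closer to the plan.** Mediators at 6 and 9 months with residual correlation 0.6; condition effect 0.3 on each; path 0.15 from each to the outcome; 5,000 trials, 700 bootstrap draws. For false positives the relevant path is set to zero. The comparator is the same bootstrap on fully observed cases.

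- Mediators and outcome missing together: condition-to-mediator coverage 92/90–91/88–89%. With no condition effect, the total indirect effect excludes zero in 8.3/9.6/11.6% of trials, against 5.5–5.7%.
- Half of the 9-month dropouts also missing 6 months: 9-month path coverage 93/91/90%; false positives 6.6/8.0/8.6%, against 4.9–5.5%.
- Outcome only missing: mediator-to-outcome coverage 92/90/88%. With no mediator-to-outcome effect, false positives are 7.0/8.1/9.5%, against 3.8–4.3%.

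**Survey missing, HbA1c present.** The withdrawal options and record extraction allow this; its frequency is not given. Exact population values under the two-mediator model: if 5/10/15/20% miss both surveys, both mediator-to-HbA1c paths and the total indirect effect move about 5/10/16/23% away from zero. If 5% miss only the 9-month survey, the 9-month path rises 5%, the 6-month path falls 3% and the total rises 1%.

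**The case against.** The strongest objection is that the defect is inferred. The SAP names a software function without describing it, and the remark about running imputations separately by model is ambiguous. If values were re-imputed in each bootstrap sample, or stochastic draws were pooled, coverage would be about nominal and the fault would be one of reporting. That stands as a condition on the size of the problem. But the SAP spells out multiplicity for chained equations and not here, so a single fill is the natural reading, and the text needs correcting either way.

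It can also be said that a specific rule governs a general one, and that the time-split imputation models explain why SEM needed its own. That is plausible and weakens the charge of contradiction. The SAP says neither thing, however, and a choice of method for SEM does not excuse a method that ignores imputation uncertainty.

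Third, mechanism claims rest on indirect effects, which usually lose less than single paths. This is true: 90–94% in the first two rows of the table. It does not hold where it matters most for false claims: at 20% missing, with either component path truly zero, indirect-effect coverage falls to about 89%.

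Fourth, mediators are restricted using the findings on intervention effects, which limits false mediators with no condition effect; the first two false-positive settings ignore this screening. Screening gives no protection when condition moves the mediator, the mediator does not affect the outcome, and only the outcome is missing.

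Finally, the rates are planning values. Record HbA1c may reduce outcome-only gaps. Distress and well-being at 9 months share a survey with the 9-month mediators, which favours joint missingness, where the mediator-to-outcome path stays nominal. Both points are fair, and are why the actual counts should be reported.

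**Conclusion.** The concern holds. As written, the mediation analysis fills missing values by regression imputation and bootstraps the result, with nothing stated that carries imputation uncertainty, and the method is not reconciled with the general M=500 rule. On the natural reading, affected paths have about 92/90/88% coverage instead of 95% at 10/15/20% missing. False-positive mediation rises by about 1.5 to 6 points in the two-mediator settings. Where surveys are missing but HbA1c is present, the total indirect effect is also biased away from zero, by an amount that depends on an unknown frequency.

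The coverage and false-positive figures rest on a single deterministic fill, data missing completely at random and the assumed path values; the missingness rates come from planning assumptions. Only Aim 4 is affected. The HbA1c, secondary-outcome and intervention-target effects come from separate GEE or ordinal models. The point should be fixed before the mediation results are relied on; confidence in its practical size is moderate.

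**What to change.** State in the SAP which missing-data rule governs the SEM, how many imputations are made, whether residuals are drawn, and how imputation and bootstrap are combined. Then replace the regression imputation with one of:

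1. multiple imputation from a model joining the 6- and 9-month mediators to the 9-, 12- and 15-month outcomes, with pooled results;
2. stochastic imputation repeated inside each bootstrap sample;
3. full-information maximum likelihood with bootstrap or Monte Carlo intervals.

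In the one-mediator simulation, re-imputing fitted values inside each bootstrap sample gave 93–96% coverage for joint and outcome-only missingness. Mediator-only missingness was not tested; there, residual draws are needed as well because fitted values bias the path. Pooled multiple imputation with 100 imputations gave 94.4/94.5/95.1% for the condition-to-mediator path. One stochastic imputation without pooling is not enough: affected paths stayed at about 92/90/88%.

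Also report how many participants have HbA1c but no survey at 6 and at 9 months, and how many have mediators but no 12- or 15-month outcome, so that readers can see which pattern dominates.

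The cost is SAP wording, a re-run of the path models and more computing time. No new data are needed. Intervals will be wider, and some indirect effects may no longer exclude zero.
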